8.2 Data quality and assurance

This NIS is conducted in accordance with sections 4.23 and 67.6 of the Medicines Act of the Federal Republic of Germany (AMG) and the recommendations of the Federal Institute for Drugs and Medical Devices and the Paul-Ehrlich Institute for the planning, conduct and evaluation of postmarketing surveillance studies, as well as relevant BI standard operating procedures (SOPs).

The data from the NIS mentioned under 6.2 will be recorded on internet-based electronic documentation forms (eCRF). All documentation forms in the eCRF must be completed in full.

All entries in the eCRF and the existing codings will be stored in a database. The structure of the database is based on the division into sections and entry fields defined in the eCRF. The patient questionnaires are entered directly into the database via entry masks at the CRO.

To improve and ensure data quality, data checks will be performed automatically in the eCRF directly on electronic entry at the trial site: plausible value ranges for numerical data entries and logical data and list entries will be filed in the eCRF. The tests for consistency and completeness based on this will be performed during entry in the eCRF. The validity of the recorded data will therefore be ensured by the validations incorporated in the documentation system, which highlight incorrect or implausible entries to the data entry clerk/doctor.

If corrections are necessary after the data are input, these will be documented in an audit trail.

For the further quality assurance of the documented patient observations, a sample-based source data comparison will be performed on about 10% of the sites, in the course of which the documented data will also be checked on site for completeness and consistency. An additional inspection/quality assurance check of this NIS can be performed.

8.2.1 Data protection

Before patients can be included in this NIS, they will be given an explanation of the processing of personal data and comprehensively informed about the transmission of their data to third parties concerned. They will be asked to give their written consent to this.

Patient data will be recorded in pseudonymous form. A list of patients who have given their consent to participate in the NIS will be kept for each site. This list will be kept confidentially in the study folder. Patient allocation is done on the basis of year of birth and the patient number issued at the participating trial site.

All information collected during the NIS will be treated confidentially at all times. Previous history data and data on therapeutic measures, emergent side effects and disease course will be obtained from patients in the course of this NIS.

All the recorded data will serve to answer the above-mentioned questions and will be recorded at the trial site using an electronic documentation system (eCRF) from

8.3 Documentation of the NIS

The Morisky questionnaire completed by the patient as part of visit 3 is sent to the attendant CRO, where it is entered in the database.

All other data from the NIS mentioned under 6.2 will be recorded in an electronic documentation system (eCRF).

8.3.1 Source data

All participating doctors are obliged to record patients' participation in the NIS in the patients' original documents.

In the event of any queries, the participating doctor must be able to identify the observed patient.

Medical information about patients may only be communicated and analysed under the patients' number.

8.3.2 Direct access to source data and documents

By signing the contract, the participating site has consented to source data verification, which will take place at the participating sites.

For quality assurance of the documented patient observations, a source data comparison is undertaken sample-based on about 10% of the sites, following which the documented data are also checked on site for completeness and consistency.

8.3.3 Archiving of documents

The observing physician will keep the original documents in accordance with the statutory retention time.

All study-specific documents will be archived by Boehringer Ingelheim Pharma GmbH & Co. KG for a period of 10 years after the end of this NIS.

8.4 Listing and accelerated reporting procedure of adverse events

As the marketing authorisation holder of Pradaxa[®], Boehringer Ingelheim International GmbH is responsible for the accelerated reporting of serious adverse events, such as SUSARs, in accordance with the currently applicable statutory requirements.

Attachment 1: Morisky questionnaire

NIS 1160.xxx:

**Drug persistence/adherence in patients being treated with
Pradaxa® (dabigatran etexilate) or vitamin K antagonists (VKA)
for stroke prevention
in non-valvular atrial fibrillation (AF)**

Site number: _____

Patient number: _____

Visit 3, date: _____

Dear patient,

You have said that you are taking medicine for stroke prevention in atrial fibrillation.

Some patients have experienced various problems associated with their medication-taking behaviour and we are interested to find out about your experiences.

There are no right or wrong answers.

Please answer each question on the basis of your personal experience with your medicine for stroke prevention in atrial fibrillation.

Please tick the answer that applies		No	Yes
1.	Do you sometimes forget to take your stroke prevention tablets?		
2.	People sometimes miss taking their medicines for reasons other than forgetting. Thinking over the past 2 weeks, were there any days when you did not take your medicine for stroke prevention?		
3.	Have you ever cut back or stopped taking your medicine without telling your doctor because you felt worse when you took it?		
4.	When you travel or leave home, do you sometimes forget to bring along your medicine for stroke prevention?		
5.	Did you take your medicines for stroke prevention yesterday?		
6.	When you feel like your stroke prevention is under control, do you sometimes stop taking your medicine?		
7.	Taking medicine every day is a real inconvenience for some people. Do you ever feel hassled about sticking to your treatment plan?		
Please tick the answer that applies		Never/rarely	Once in a while
1.	How often do you have difficulty remembering to take all your medicine?		
		Sometimes	Usually
		All the time	

© Morisky Medication Adherence Scale (MMAS-8-item) German

BI No.: 1160.218

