1.1 Medical background

Atrial fibrillation (AF) is a cardiac rhythm disorder that can occur episodically or persistently. During AF, unco-ordinated electromechanical activity of the cardiac atria occurs, triggered by rapidly succeeding, disorderly impulses that can in some cases be transmitted to the cardiac ventricles. AF is the most common cardiac arrhythmia and is associated with considerable morbidity and mortality, due in particular to a 4- to 5-fold increase in the risk of thromboembolic strokes (1).

Due to the high thromboembolic risk in atrial fibrillation, it is a fundamental aim of treatment to reduce the secondary complications associated with atrial fibrillation and in particular the risk of stroke. Oral anticoagulation is usually recommended for this purpose (1;2). In Germany, phenprocoumon is most frequently used for anticoagulation with a vitamin K antagonist (VKA) (3).

In order to maintain the level of therapeutic anticoagulation within an optimum target range during treatment with VKA, the coagulation capacity of the blood must be closely monitored (i.e. at least every 3 – 4 weeks) by means of the INR value (4). This usually requires a visit to a physician, who can take a blood sample and perform the analysis (where necessary also via an external laboratory) and any dosage adjustment necessary.

The use of VKA is associated with various measures that can make it more difficult to use these drugs correctly. The narrow therapeutic window of VKA requires routine laboratory monitoring of coagulation (INR 2-3). However, optimal INR adjustment is often not obtained in everyday patient care in Germany either. The interactions of VKA with a number of medicines and foodstuffs require close monitoring and dosage adjustments following a change of concomitant medication or dietary habits. A recent analysis of German health insurance data came to the conclusion that AF patients with a moderate stroke risk and without any observable contraindication to OACs received no OAC on up to half the patient days observed (5).

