Dabigatran etexilate differs from VKA in that it does not intervene in the hepatic synthesis of coagulation factors, but indirectly competitively inhibits a specific plasma factor. Routine monitoring in the form of coagulation tests is required during therapy with VKA, as opposed to with the use of dabigatran etexilate, because the therapeutic margin of VKA is small and the anticoagulant effect can be affected by many interactions with other medicinal products, but also with certain foodstuffs (9, 10).

The pharmacodynamic effect of dabigatran sets in rapidly and also declines rapidly and therefore is easily controllable and predictable. That is an essential difference from the VKA, which only become effective after a few days if the concentration of vitamin K-dependent coagulation factors has declined sufficiently and only become ineffective after a few days if there is once again sufficient production of these factors in the liver.

2 Rationale, objectives and risk-benefit analysis

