2.1 Rationale for conducting the study

As well as the challenges described above, treatment compliance (persistence and adherence) represents a significant factor affecting the success of treatment (11).

Persistence is defined as the time between initiation and termination of therapy (12). Adherence describes whether patients take their medicine as prescribed. It comprises the initiation, implementation and termination of therapy (13). This compliance can be determined on the basis of the Morisky questionnaire. This consists of questions relating to intake behaviour (14). The questionnaire and its further developed version have already been used for assessing adherence during warfarin therapy, where it exhibited good validity (15, 16).

There are a variety of reasons for poor treatment compliance. These include patient-related aspects (e.g. socioeconomic status, personal convictions), but also disease-related (e.g. symptom severity) and medication-related (e.g. frequency of intake, side effects) aspects (17). This also applies particularly to patients with AF who require permanent oral anticoagulation (18). In terms of anticoagulation for the prevention of strokes, one important aspect is the fact that in the patients' subjective view it does not improve their condition and only the absence of a negative event (e.g. stroke) motivates them to continue treatment. This could limit treatment compliance and reduce the acceptance of side effects.

In addition, it has not yet been elucidated whether omission of the routine monitoring of coagulation status during treatment with dabigatran etexilate and the associated feedback to patients has any effect on treatment adherence in everyday therapeutic use. An analysis of Canadian health insurance data shows that drug persistence following the initiation of everyday care is higher during treatment with dabigatran etexilate than during VKA therapy (19).

No studies have yet been undertaken as to whether there are differences in persistence and adherence within the German care context between patients treated with Pradaxa® or VKA. For this reason, a contribution to the resolution of this question constitutes a relevant gain in knowledge.

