7.5 SECONDARY ENDPOINT(S)

Absolute number and percentage of patients, who discontinue the initial treatment during study, will be summarized collectively and according to reasons for discontinuation for the dabigatran etexilate and VKA cohort, respectively.

The analysis of secondary endpoints will be based on the patient cohort resulting from the 1:1 matching.

The Morisky questionnaire consists of 8 question and will be answered at the 6- months visit. Each question can be scored with 0 or 1. For questions 1-7, 'no' will be scored with 0 and 'yes' with 1. For question 8, 'None/rarely' will be scored with 0 and all other answers with 1. The Morisky score is given by the sum of the values of each question, which implies a score between 0 and 8.

The categorisation of patients into low adherence (score >2), medium adherence (score=1,2) and high adherence (score=0) is done according to Morisky. The score will only be calculated for patients who answered all eight questions. In case that the proportion of the patients who did not answers all questions is too high (i.e. >20%) a sensitivity analysis will be conducted in which the score will be calculated if up to 2 questions per patient are missing. Patients who changed their initial treatment or withdrew from the study before the 6-months visit, will be displayed seperately from those for which the Morisky score could not be calculated for other reasons. Patients with missing data will be analyzed regarding to their baseline characteristics in comparision to the patients with an evaluable Morisky score; patients with missing values at the 6-months visit will be stratified into (i) the groups of study drop-outs, (ii) treatment drop-outs and (iii) patients with missing values because of other reason. The last mentioned analyses will only be done for strata of at least 200 patient (overall and for each treatment group).

Number and percentage of patients within the different adherence classes will be displayed for dabigatran etexilate and VKA patients, respectively. Furthermore the following subgroups will be presented for adherence (overall and for each treatment group):

- CHA₂DS₂-VASc-Score (<2, ≥2)
- Age (<65, 65- <75, ≥75)
- Previous stroke Yes, No)
- Medical specialty of attending physician (Internist, Cardiologist, General practitioner, Other)
- Daily dose of Pradaxa® at initial visit (2x110mg daily, 2x150mg daily) [Patients treated with Pradaxa® only]
- HAS-BLED-Score (<3, ≥3).

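### Item 7 of the Morisky questionnaire scores a feeling of burden as reduced adherence, so the adherence classes can differ between the drugs with identical intake; direction and size are unknown

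*Protocol*

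**What the plan says.** Protocol 2.1 defines the construct: "Adherence describes whether patients take their medicine as prescribed". Protocol 5.3 likewise presents the questionnaire as a measure of intake behaviour. Comparing adherence between the drugs is a secondary objective (Protocol 2.2).

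Item 7 in Attachment 1 is worded differently from most of its neighbours. It reads: "Taking medicine every day is a real inconvenience for some people. Do you ever feel hassled about sticking to your treatment plan".

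SAP 7.5 sets the scoring: "For questions 1-7, 'no' will be scored with 0 and 'yes' with 1". The eight items are summed; 0 is high, 1 or 2 is medium, and more than 2 is low. Protocol 7.3 has the same cut-offs.

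On the two regimens, Protocol 1.2 says: "Routine monitoring in the form of coagulation tests is required during therapy with VKA, as opposed to with the use of dabigatran etexilate". Protocol 1.1 says that coagulation under VKA "must be closely monitored (i.e. at least every 3 – 4 weeks) by means of the INR value". Protocol 4.1.3 describes dabigatran as one capsule twice daily and gives no intake frequency for VKA.

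The planned output is the number and percentage in each class by drug, overall and in subgroups. The only sensitivity analysis of the score concerns unanswered questions. Neither document plans a table of item responses or a check that the score behaves alike under both drugs.

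**The concern.** A patient who never misses a dose can truthfully say that the regimen is a hassle. That answer costs a point in a score that is read as intake. If the score were used within one drug, this would be a feature of the scale and little more. Here it compares two drugs whose regimens differ in the kind of burden they impose, so the measurement itself may work differently in the two groups. Propensity score matching balances baseline characteristics and cannot remove a difference that arises from how the outcome is measured.

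The protocol also names an unresolved question, namely if "omission of the routine monitoring of coagulation status during treatment with dabigatran etexilate and the associated feedback to patients has any effect on treatment adherence". If the nuisance of monitoring can enter the adherence score directly, the exposure of interest and the outcome overlap on that question. With only three classes per drug on display, a reader could not tell a difference in missed doses from a difference in how burdensome patients find the regimen.

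**Working it through.** The documents give no expected rate, sample size or power for adherence, so there is no stated figure to reproduce. The check applies the SAP scoring rule and then illustrates size under labelled assumptions.

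**Step 1. When does item 7 change the class?** Let S be the score on the other seven items. A yes to item 7 turns S into S + 1. With the cut-offs in SAP 7.5 the class changes only if S = 0 (high to medium) or S = 2 (medium to low). The seven items have 2^7 = 128 answer patterns. S = 0 occurs in 1 pattern and S = 2 in C(7,2) = 21, so the class changes in 22 of 128. These are counts of patterns, not of patients.

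**Step 2. The role of item 5.** Item 5 asks whether the medicine was taken the day before, so the adherent answer is yes. SAP 7.5 scores that yes as 1. For a patient with perfect intake:

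| Scoring of item 5 | Item 7 no | Item 7 yes |
|---|---|---|
| As SAP 7.5 is written (yes = 1) | 1, medium | 2, medium |
| Reversed (no = 1) | 0, high | 1, medium |

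Under the literal scoring, the single high-to-medium pattern belongs to a patient who says the medicine was *not* taken the day before. Nobody who took it can be high, and for them item 7 matters only at the medium/low boundary: C(6,1) = 6 of their 64 patterns move from medium to low, and none from high. Reversing item 5 leaves the total of 22 patterns unchanged, but the high-to-medium pattern then belongs to the patient with perfect intake.

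**Step 3. Size, with item 5 reversed.** Let p0 be the share scoring 0 on the other seven items, equal in both groups because intake answers are taken as identical. Let hV and hD be the shares of those patients who answer yes to item 7 on VKA and dabigatran.

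High adherence = p0 × (1 − h) in each group, so the artefact = p0 × (hV − hD).

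None of these rates is in the documents. Assume p0 of 40% to 60%, with 10% yes in one group and 15% to 30% in the other:

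| p0 | 10% vs 15% | 10% vs 25% | 10% vs 30% |
|---|---|---|---|
| 40% | 2.0 points | 6.0 points | 8.0 points |
| 50% | 2.5 points | 7.5 points | 10.0 points |
| 60% | 3.0 points | 9.0 points | 12.0 points |

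For example, p0 = 50% with 10% against 25% gives 0.50 × 0.90 = 45.0% and 0.50 × 0.75 = 37.5%. Swapping the groups reverses the sign. If hV = hD the artefact is zero. The range moves with the assumptions: p0 = 80% with 10% against 30% would give 0.80 × 0.20 = 16 points.

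At the medium/low boundary the same logic gives (share with S = 2) × (difference in yes to item 7 among them), under either scoring of item 5.

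**Step 4. Without item 7.** If the other seven items are distributed identically, the difference in every class is zero.

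**The case against.** The study uses an established eight-item scale with its own classes and cites good validity in patients on warfarin. Removing an item while keeping the cut-offs creates a score that has not been validated. This stands, and it is why the eight-item classes should remain the endpoint. The cited validity does not settle the matter, however: neither Protocol 2.1 nor 5.3 cites validity for dabigatran or for comparing the two drugs.

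The endpoint is secondary, the study is descriptive, and no test of adherence is planned. This also stands, and it limits how much weight the point can carry. It does not make a difference of unknown origin easier to interpret.

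A reader might infer that the item favours dabigatran, since only VKA carries routine monitoring. The documents do not support that. Item 7 opens with daily intake, the form asks patients to answer about their stroke-prevention medicine, and dabigatran is taken twice daily. Protocol 2.1 itself lists intake frequency and side effects among the reasons for poor compliance. Yes answers could be more common on either drug.

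A reader might also infer that, under the SAP as written, item 7 takes high adherence away from patients with perfect intake. It does not, because the literal scoring of item 5 already keeps them out of that class.

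Finally, item 8, on difficulty remembering, does not record a missed dose either. A seven-item score is therefore closer to intake but is not a pure measure of it.

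**Conclusion.** The point holds as a measurement concern of moderate weight. Item 7 measures perceived burden, carries a full point, and sits in a score used to compare drugs with different burdens. The adherence classes can therefore differ between the drugs with identical intake, and nothing in the planned output would show it.

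The size of about 2 to 12 points in high adherence, in either direction, rests wholly on assumed rates and on item 5 being reverse-scored. It is zero if item 7 answers do not differ between the drugs. With item 5 scored as SAP 7.5 now has it, the effect lies mainly at the medium/low boundary. The documents do not show that such a difference will arise.

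It might be tempting to conclude that a difference which disappears without item 7 must be one of burden. That does not follow: chance or the coarser seven-item score could also remove it, and no test is planned that would define when a difference is present.

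**What to change.** In SAP 7.5:

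1. Correct the scoring of item 5 first, so that no = 1 and yes = 0. Without this, a display that omits item 7 would still bar anyone who took the medicine the day before from the high class.
2. Keep the eight-item classes as the secondary endpoint.
3. Add a table of the responses to all eight items by drug in the matched group.
4. Add a supplementary three-class display without item 7 (items 1 to 6 and 8, item 5 reversed; 0 high, 1 to 2 medium, more than 2 low).
5. State that a between-drug difference in the eight-item classes will be interpreted alongside these two displays, and will not be attributed to medication intake alone if item 7 drives it.

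The cost is a few sentences in the SAP and two tables from data already collected. The drawback is that the seven-item version is not the published scale. With one item fewer and the same cut-offs it can only place patients in the same class or a better one, so its levels should not be set against the eight-item levels. Only the contrast between the drugs is informative, and it is supportive.

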Attachment 2: (S)AE form

Please send immediately to Boehringer Ingelheim Pharma GmbH & Co KG on [contact] or [contact]. Leave shaded areas blank.

 Boehringer Ingelheim		Report of Serious/Non-Serious Adverse Events in Non-Interventional Study (NIS) NIS title: 1160.218 / Pradaxa®					OPU case ID number:		Reporter name / telephone and fax number		
Site number: _____							Pat. initials: _____	Pat. No.: _____	BI CTMS number: 1160.218		
Sex 1  male 2  female	Date of birth (Day / Month / Year) _____		Age _____	Height (cm) _____	Weight (kg) _____ . _____	Race 1  White 2  Black 3  Asian	Pregnant 0  no 1  yes Week: _____				
 Initial report  Follow-up report		Date of the event (enter date for each event)			Intensity of the event 1= mild 2= moderate 3= severe	Therapy of the event 0= no 1= yes	As a result of the event, adminis- tration of the BI product was: 1= continued 2= reduced 3= discontinued 4 = increased 5= terminated in line with observational plan 6= discontinued and resumed 7 = not applicable	Outcome of the event 1= recovered 2= not yet recovered 3= permanent damage 4= fatal 5= unknown	Was the event serious? ** If fatal, please attach copy of death certificate	Causal relationship	Is the event expected (listed / expected) ?
Event: Describe all observed events, symptom(s). Also all non-serious events associated with the serious event.		If still ongoing at the end, enter "ongoing" in the 'End date' column									
		Start date Day/Mon/Year	Time in hh:mm (24-hr clock)	End date Day/Mon/Year	Time in hh:mm (24-hr clock)	If yes, please explain under descrip- tion	If yes, enter the corresponding code number 1= fatal** 2= immediately life- threatening 3= permanent or significant disability/ incapacity 4= requires hospitalisation 5= prolongs hospitalisation 6= congenital abnormality 7= other / further comparable medical criteria, e.g. drug dependence, abuse, cancer, etc.)				
1.											
2.											
3.											
4.											
Description of the events listed above (if necessary, please give the number of the event as in the above table, Event column):											

Please send immediately to Boehringer Ingelheim Pharma GmbH & Co KG on [contact] or [contact]. Leave shaded areas blank.

 Boehringer Ingelheim Site number: _____ _	Report of Serious/Non-Serious Adverse Events in Non-Interventional Study (NIS) NIS title: 1160.218 / Pradaxa®					OPU case ID number:		BI CTMS number:		
						Pat. initials: _____ _		Pat. No.: _____ _		1160.218
Drug / therapy If medicinal product, give proprietary and common name		Pharma-ceutical form	Total daily dose at start (dose, unit)	Route of administration	Start (date) Day / Month / Year	End (date) Day / Month / Year	Given for which indication?		Other suspect drug: is there a causal relationship between event and concomitant therapy?	
Boehringer Ingelheim medication Pradaxa®									Reporter: 0= no If yes, enter number of event	PV Ger: 0= no If yes, enter number of event
Concomitant therapy (relevant) 1. 2. 3. 4.										
Concurrent diagnoses (relevant): 1. 2. 3.										
Comments (surrounding circumstances, alternative explanation of the event, where applicable re-exposure, etc.) <hr/> <hr/>								Name of reporter: Signature Date <hr/> <hr/> Day / Month / Year		

Observational Plan

Non-interventional study

Local Amendment

Local Amendment Number:	Local Amendment 1	
Date:	16. APR 2015	 To be implemented only after documented approval of the IRB / IEC / Competent Authorities
EudraCT No.:	n.a.	 To be implemented immediately in order to eliminate hazard – IRB / IEC / Competent Authority to be notified of change with request for approval
BI Trial No.:	1160.218	
Investigational Product(s):	Pradaxa®	 Can be implemented without IRB / IEC / Competent Authority approval as changes involve logistical or administrative aspects only
Title:	Drug persistence/adherence in patients being treated with Pradaxa® (dabigatran etexilate) or vitamin K antagonists (VKA) for stroke prevention in non-valvular atrial fibrillation (AF)	
Rationale for Local Amendment:	
After 6 months of site and patient recruitment it became evident that the targeted patient and site numbers will not be met and that recruitment time should be longer.
 
Therefore the planned patient number will be reduced to 1600 and site number to 800.
 
Recruitment time will be prolonged to 16 months (LPI December 2015), thus study duration will also increase. LPO is now planned for December 2016.
 
Other timelines will change accordingly.
 
New site and patient numbers will be used as calculation basis in the statistical analysis plan.
 
As this amendment is administrative and does not change the content or the nature of this non-interventional study, for readability reasons we refrain from changing every sentence in which site numbers, patient numbers or timelines are mentioned, except for the front page, study synopsis and statistics section.
	
Page 1 of 5		

Proprietary confidential information. © 2015 Boehringer Ingelheim International GmbH or one or more of its affiliated companies. All rights reserved. This document may not - in full or in part - be passed on, reproduced, published or otherwise used without prior written permission.
		

SIGNATURE PAGE(S)

This amendment

- concerns administrative matters only so that the coordinating investigator's signature will not be obtained.
- concerns matters dealing with design elements of the study, in- / exclusion criteria, observations, or safety or efficacy related study elements so that the coordinating investigator's signature needs to be obtained.

Trial Clinical Monitor

May 06 2015
Date

Trial Statistician

Boehringer Ingelheim
Biometrics & Data
Management

Team Member Medicine

Boehringer Ingelheim
Corporate Medical Affairs

Local Clinical Monitor

May 06 2015
Date

Boehringer Ingelheim
Medical Affairs Germany

SIGNATURE PAGE(S)

This amendment

concerns administrative matters only so that the coordinating investigator's signature will not be obtained.

concerns matters dealing with design elements of the study, in- / exclusion criteria, observations, or safety or efficacy related study elements so that the coordinating investigator's signature needs to be obtained.

Trial Clinical Monitor

May 06 2015

Date

Trial Statistician

May 07 2015

Date

Boehringer Ingelheim
Biometrics & Data
Management

Team Member Medicine

Date

Boehringer Ingelheim
Corporate Medical Affairs

Local Clinical Monitor

May 06 2015

Date

Boehringer Ingelheim
Medical Affairs Germany

SIGNATURE PAGE(S)

This amendment

- concerns administrative matters only so that the coordinating investigator's signature will not be obtained.
- concerns matters dealing with design elements of the study, in- / exclusion criteria, observations, or safety or efficacy related study elements so that the coordinating investigator's signature needs to be obtained.

Trial Clinical Monitor

May 06 2015

Date

Trial Statistician

Date

Boehringer Ingelheim
Biometrics & Data
Management

Team Member Medicine

J. S. 2015

Date

Boehringer Ingelheim
Corporate Medical Affairs

Local Clinical Monitor

May 06 2015

Date

Boehringer Ingelheim
Medical Affairs Germany

CHANGE 1: ADAPT TIME SCHEDULE, SITE NUMBERS AND PATIENT NUMBERS

Section of the protocol: Front page

Scheduled time frame of the NIS:	FPI September 2014	LPO April 2016
---	--------------------	----------------

Was changed to:

Scheduled time frame of the NIS:	FPI September 2014	LPO December 2016
---	--------------------	-------------------

Reasons for change 1:

After 6 months of site and patient recruitment it became evident that the targeted patient and site numbers will not be met and that recruitment time should be longer.

Recruitment time will be prolonged to 16 months (LPI December 2015), thus study duration will also increase. LPO is now planned for December 2016.

CHANGE 2: ADAPT TIME SCHEDULE, SITE NUMBERS AND PATIENT NUMBERS

Section of the protocol: Synopsis

Target group (sites)	1000: about 670 community-based primary care internists or general practitioners and 330 cardiologists
	
• In this NIS, information about dabigatran etexilate/VKA persistence and adherence will be collected in 4000 AF patients.
Number of patients:	4000; 2000 on dabigatran etexilate; 2000 on VKA
Scheduled study duration	Initiation (FPI): September 2014 Last patient out (LPO): April 2016
Report	Report available: July 2016

Was changed to:

Target group (sites)	800: about 550 community-based primary care internists or general practitioners and 250 cardiologists
	
 • In this NIS, information about dabigatran etexilate/VKA persistence and adherence will be collected in 800 AF patients.
Number of patients:	Approx. 1600; Approx. 800 on dabigatran etexilate; approx. 800 on VKA
Scheduled study duration	Initiation (FPI): September 2014 Last patient out (LPO): December 2016
Report	Report available: March 2017

Reasons for change 2:

After 6 months of site and patient recruitment it became evident that the targeted patient and site numbers will not be met and that recruitment time should be longer.

Therefore the planned patient number will be reduced to 1600 and site number to 800.

Recruitment time will be prolonged to 16 months (LPI December 2015), thus study duration will also increase. LPO is now planned for December 2016.

Other timelines will change accordingly.

CHANGE 3: ADAPT TIME SCHEDULE, SITE NUMBERS AND PATIENT NUMBERS

Section of the protocol: Statistics Section Determination of number of patients

It is planned to include a total of 4000 patients in this non-interventional, controlled, observational study (dabigatran etexilate: 2000 patients, VKA: 2000 patients).

Calculation of statistical power:

All analyses are purely exploratory by virtue of the non-interventional study design. On the following assumptions:

- 15% drop-outs /missing values after one year,
- 2000 dabigatran etexilate patients, 2000 VKA patients, with 66% of VKA patients with a matching partner in the dabigatran etexilate group (i.e. total number of patients in the 1:1 matched analysis is 2640)
- a persistence rate of 63% in the dabigatran etexilate group (cf. 1-year persistence with a 60-day permissible medication gap as reported by Zalesak ¹⁹)).

the power for a descriptive p value ≤ 0.05 in a 2-tailed test for the same persistence rates is as follows (dependent on the VKA persistence rate):

Assumed VKA persistence rate*	51%	53.8%	56.5%
Power	100%	99.7%	91.7%

* The calculations were performed with ADDPLAN6 and are based on survival time analysis test statistics and the endpoint variables "Time to permanent treatment discontinuation".

Was changed to:

It is planned to include a total of 1600 patients in this non-interventional, controlled, observational study (dabigatran etexilate: 800 patients, VKA: 800 patients).

Calculation of statistical power:

All analyses are purely exploratory by virtue of the non-interventional study design. On the following assumptions:

- 15% drop-outs /missing values after one year,
- 800 dabigatran etexilate patients, 800 VKA patients, with 66% of VKA patients with a matching partner in the dabigatran etexilate group (i.e. total number of patients in the 1:1 matched analysis is 1056)
- a persistence rate of 63% in the dabigatran etexilate group (cf. 1-year persistence with a 60-day permissible medication gap as reported by Zalesak (¹⁹)).

the power for a descriptive p value ≤ 0.05 in a 2-tailed test for the same persistence rates is as follows (dependent on the VKA persistence rate):

Assumed VKA persistence rate*	51%	53.8%	56.5%
Power	97.8%	84.8%	61.1%

* The calculations were performed with ADDPLAN6 and are based on survival time analysis test statistics and the endpoint variables "Time to permanent treatment discontinuation".

Reasons for change 3:

After 6 months of site and patient recruitment it became evident that the targeted patient and site numbers will not be met and that recruitment time should be longer.

Therefore the planned patient number will be reduced to 1600 and site number to 800.

Observational Plan

Non-interventional study

Local Amendment

Local Amendment Number:	Local Amendment 2			
Country	Germany			
Date:	04. JAN 2016	 To be implemented only after documented approval of the IRB / IEC / Competent Authorities		
EudraCT No.:	n.a.	 To be implemented immediately in order to eliminate hazard – IRB / IEC / Competent Authority to be notified of change with request for approval		
BI Trial No.:	1160.218			
Investigational Product(s):	Pradaxa®	 Can be implemented without IRB / IEC / Competent Authority approval as changes involve logistical or administrative aspects only		
Title:	Drug persistence/adherence in patients being treated with Pradaxa® (dabigatran etexilate) or vitamin K antagonists (VKA) for stroke prevention in non-valvular atrial fibrillation (AF)			
Rationale for Local Amendment:	
After 15 months of patient recruitment 1050 / 1600 patients have been included until December 2015. For a meaningful data analysis and interpretation, the targeted patient number of 1600 patients should be met.
 
Therefore, recruitment time will be prolonged for one more year to 27 months (LPI December 2016), thus study duration will also increase. LPO is now planned for December 2017.
 
Other timelines will change accordingly.
 
In case 1600 patients will be included earlier, recruitment may be stopped before December 2016.
 
As this amendment is administrative and does not change the content or the nature of this non-interventional study, for readability reasons we refrain from changing every sentence in which site numbers, patient numbers or timelines are mentioned, except for the front page, study synopsis and statistics section.
			
Page 1 of 3				
Proprietary confidential information. © 2016 Boehringer Ingelheim International GmbH or one or more of its affiliated companies. All rights reserved. This document may not - in full or in part - be passed on, reproduced, published or otherwise used without prior written permission.				

SIGNATURE PAGE(S)

This amendment

concerns administrative matters only so that the coordinating investigator's signature will not be obtained.

concerns matters dealing with design elements of the study, in- / exclusion criteria, observations, or safety or efficacy related study elements so that the coordinating investigator's signature needs to be obtained.

Trial Clinical Monitor

14.01.16

Date

Boehringer Ingelheim
Medical Affairs Germany

Trial Statistician

Date

Boehringer Ingelheim Biometrics & Data Management

Team Member Medical Affairs

18-01-2016

Date

Boehringer Ingelheim
Corporate Medical Affairs

Local Clinical Monitor

14. 01. 16

Date

Boehringer Ingelheim
Medical Affairs Germany

SIGNATURE PAGE(S)

This amendment

- concerns administrative matters only so that the coordinating investigator's signature will not be obtained.
- concerns matters dealing with design elements of the study, in- / exclusion criteria, observations, or safety or efficacy related study elements so that the coordinating investigator's signature needs to be obtained.

Trial Clinical Monitor

14.01.16

Date

Boehringer Ingelheim
Medical Affairs Germany

Trial Statistician

14.01.16

Date

Boehringer Ingelheim
Biometrics & Data
Management

Team Member Medical Affairs

18-01-2016

Date

Boehringer Ingelheim
Corporate Medical Affairs

Local Clinical Monitor

14.01.16

Date

Boehringer Ingelheim
Medical Affairs Germany

CHANGE 1: ADAPT TIME SCHEDULE, SITE NUMBERS AND PATIENT NUMBERS

Section of the protocol: Front page

Scheduled time frame of the NIS:	FPI September 2014	LPO April 2016
---	--------------------	----------------

Was changed to:

Scheduled time frame of the NIS:	FPI September 2014	LPO December 2017
---	--------------------	-------------------

Reasons for change 1:

After 15 months of patient recruitment 1050 / 1600 patients have been included until December 2015. For a meaningful data analysis and interpretation, the targeted patient number of 1600 patients should be met.

Therefore, recruitment time will be prolonged for one more year to 27 months (LPI December 2016), thus study duration will also increase. LPO is now planned for December 2017.

